### 3.2 Primary Study Endpoints

To assess the efficacy of Abatacept + csDMARD to induce low disease activity [DAS28-CRP (<3.2) or CDAI (<10) that can be maintained on csDMARD alone. A necessary co-primary objective is the relationship between clinical response and changes in B cell and antibody parameters that are unaffected by TNF-inhibition.

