## Study Summary

Title	Rheumatoid arthritis memory B cells and Abatacept
Short Title	RAMBA
Protocol Number	IM101-768
BMS Protocol Number	IM101-768
Phase	Phase 4
Methodology	Open label
Study Duration	12 months
Study Center(s)	Single-center
Objectives	We will test the hypothesis that ABATACEPT treatment influences the levels of circulating autoimmune anti-citrullinated protein antigen (ACPA) memory B cells are central drivers of pathogenesis.
Number of Subjects	25
Diagnosis and Main Inclusion Criteria	Adults with Seropositive (CCP or ACPA) Rheumatoid Arthritis who are Naive to Biologic Disease-Modifying Antirheumatic Drugs
Study Product, Dose, Route, Regimen	Abatacept Time 0, Week 2, Month 1, 2, 3, 4, & 5 IV administration on Abatacept (7 infusions)
Duration of administration	6 months with active therapy followed by holding Abatacept for 6 months or until flare occurs while concurrent MTX or csDMARDs are continued.
Reference therapy	
Statistical Methodology	We will assess whether ABATACEPT challenge that induces clinical benefits are paralleled by reductions (i.e.,normalization) in the in vivo representation of disease-associated anti-citrullinated protein antigen (ACPA) memory B cells, and circulating autoantibody levels after 6 months of treatment.

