### **Primary Objective**

To assess the efficacy of Abatacept + csDMARD to induce low disease activity that can be maintained on csDMARD (primarily MTX) alone. A necessary co-primary objective is the relationship between clinical response and changes in B cell and antibody parameters that are unaffected by TNF-inhibition.

To directly determine whether ABATACEPT treatment normalizes immune (i.e., B cell and antibody) abnormalities associated with seropositive RA over time and assess for correlations with clinical response measures. The investigations will include: i). Direct quantitation of the frequency of circulating ACPA-bearing memory B cells (2); ii) Flow cytometric determinations of effects on B-cell subsets, to determine whether ABATACEPT normalizes disease-associated increases in activated memory B cells, and the plasmablast expansions that are associated with active RA disease. iii) The effects of ABATACEPT on circulating IgM-, IgG- and IgG-ACPA antibody levels, in assays using a panel of matched citrulline- and arginine-containing peptides/self-proteins. iv) Serum will be collected for cytokine/chemokine profiling, which will be highly informative due to the challenge/dechallenge design.

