### 3 Study Design

#### 3.1 General Design

A phase IV open-label clinical trial in which each CCP/ACPA+ patient will be their own longitudinal control for the immunomodulatory activity of Abatacept. All patients will have blood collection, including for peripheral blood mononuclear cells (PBMC), PBMC RNA and plasma, at screening and at day 0 after which Abatacept will be initiated in concert with methotrexate or pre-existing csDMARD. Each patient will then be reevaluated at 3 months and 6 months. In all patients, Abatacept will be discontinued after 6 months. Patients who have flared or failed to achieve low disease activity at 6 months, will exit the trial except for one post study visit for lab work at 9 months.

In patients who have achieved low disease activity by DAS28-CRP (<3.2) or CDAI (<10), Abatacept will be held for 6 months or until a flare results. A flare is defined by an examination demonstrating a DAS28-CRP that is greater than an absolute value of 4.0) or a CDAI >15, both defining the mid-range of a moderate flare. Alternatively, a 30% increase in the absolute level of the DAS28-CRP or CDAI that result in measures of 3.2 and 10 respectively, will be considered evidence of a flare. If patients do not experience a flare after 6 months off Abatacept (by week 52) they will also exit the study after a final visit with an exit blood draw.

Overall, in this pilot study, patient screening will continue until 25 suitable patients are enrolled and started on therapy in the trial. We predict enrollment of 2-3 patients/month, and hence the study should be fully enrolled by month 14 with the expectation that 70-80% will achieve low disease activity at week 24 enabling 17-20

patients to be followed for flare following Abatacept dechallenge. This estimate is based on the observation that treat provides nearly 60% ACR 50 responses, despite the fact that patients were selected for evidence of erosive disease.

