#### 2. Target Population

- a) Men or women (not nursing or pregnant) over 18 years old who have active RA, defined as symptoms of RA prior to screening and have satisfied the ACR/EULAR 2010 criteria for the classification of RA prior to signing the informed consent.
- b) Subjects must have a DAS28CRP or CDAI assessment at screening and have at least 3 tender and at least 3 swollen joints (excluding distal interphalangeal joints) at screening and at Day 1. Patients must have at least moderate disease activity [CDAI>16); DAS28CRP ( $\geq 4.0$ )].
- c) Subjects must be naive to biologic DMARDs
- d) Subjects must be naive to targeted synthetic DMARDs such as tofacitinib, baricitinib, and investigational therapies for RA.
- e) Subjects receiving oral corticosteroids must be on a stable dose and at the equivalent of 10 mg prednisone daily for at least 4 weeks. Subjects may not receive an IM, IV or IA administration of a corticosteroid within 4 weeks prior to screening visit or initiation of therapy
- f) Patients with prior (including discontinued) therapy with Methotrexate and/or Hydroxychloroquine are permitted as long as they meet other inclusionary criteria.
- g) Subjects must have a DAS28CRP or CDAI at screening and have at least 3 tender and at least 3 swollen joints (excluding distal interphalangeal joints) at screening and at Day 1.

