### **4.3     *Subject Recruitment and Screening***

Eligibility will be based on specified inclusion and exclusion criteria, medical history, disease activity and safety assessments. Day 1 must occur within 28 days of signing the informed consent. Subjects that experience an acute infection or initiate treatment for latent TB may extend the screening period to 42 days.

Eligible subjects will have had symptoms and diagnosis of RA prior to signing the informed consent. Symptoms of RA are defined as pain, stiffness or swelling in joints which are typically inflamed in RA. Subjects must also have fulfilled criteria for rheumatoid arthritis by ACR/EULAR 2010 classification prior to signing informed consent.

Subjects treated with MTX must remain on a stable dose of oral methotrexate for at least 4 weeks prior to Day 1. The stable dose of oral MTX should be the maximum tolerated dose (minimum of 15 mg and maximum of 25 mg per week). A dose of methotrexate 7.5-12.5mg/week is permitted if intolerance to 15 mg or higher doses has been recorded in the source documents and the dose of oral methotrexate is stable for 4 weeks prior to randomization.

To minimize potential methotrexate toxicity, all subjects must receive folic acid, folinic acid, or leucovorin according to the manufacturer recommendations, methotrexate label instructions, and the local medical standard of care guidelines. Subjects receiving oral corticosteroids must be on a stable dose and at the equivalent of 10 mg prednisone daily for at least 4 weeks prior to randomization. Subjects may not have received an IM, IV or IA administration of a corticosteroid within 4 weeks prior to randomization.

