## **5.5     *Prior and Concomitant Therapy***

Patients with newly diagnosed or established seropositive active RA will be allowed to enter this clinical trial that meet the above inclusion and exclusion criteria. The

ideal candidate for this trial is newly diagnosed RA about to be initiated on weekly methotrexate therapy (20 mg/week or the maximally tolerated dose). Prior or concurrent therapy with methotrexate or hydroxychloroquine ( $\leq$  400 mg/d). Established treatment (>4 weeks) with daily Prednisone ( $<10$  mg/d) is permitted.

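### The endpoint is maintenance on csDMARD alone, but successes are counted without regard to background prednisone or to steroid given after baseline

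*Combined protocol and SAP*

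**What the plan says.** The Primary Objective in section 2 is "low disease activity that can be maintained on csDMARD (primarily MTX) alone", and section 3.2 repeats this as the primary endpoint: low disease activity "that can be maintained on csDMARD alone". The Study Summary describes the second half of the trial as "followed by holding Abatacept for 6 months or until flare occurs while concurrent MTX or csDMARDs are continued"; corticosteroid is not mentioned there.

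Steroid appears in three places, all concerned with entry:

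- Section 4.1, Target Population item (e): "Subjects receiving oral corticosteroids must be on a stable dose and at the equivalent of 10 mg prednisone daily for at least 4 weeks". Section 4.3 repeats the requirement.
- Section 4.1, same item: "Subjects may not receive an IM, IV or IA administration of a corticosteroid within 4 weeks prior to screening visit or initiation of therapy". Section 4.3 has a parallel rule: "Subjects may not have received an IM, IV or IA administration of a corticosteroid within 4 weeks prior to randomization".
- Section 5.5, the only section on concomitant therapy, permits "Established treatment (>4 weeks) with daily Prednisone" below 10 mg a day.

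Section 3.1 sets the Month 6 gate: "In patients who have achieved low disease activity by DAS28-CRP (<3.2) or CDAI (<10), Abatacept will be held for 6 months" or until flare. Flare is a DAS28-CRP above 4.0, a CDAI above 15, or a 30% rise that brings the scores to 3.2 and 10 respectively. Section 6.3 analyses all treated subjects, and section 6.2 contains no rule, stratum or sensitivity analysis for steroid use.

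**The concern.** The protocol bars injected steroid for 4 weeks before entry, so it accepts that recent steroid can distort the disease-activity scores. The same scores then decide who is a responder at Month 6 and who flares afterwards, and no such window applies at those points. Nor does any section require the oral dose to stay unchanged after Day 1, or count a steroid start, increase or injection as failure or flare.

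The trial is open label and each patient is his or her own control, so no comparator arm absorbs a change in steroid after baseline. Low disease activity helped by an injection would be credited to abatacept at Month 6. A flare averted by added steroid would be credited to csDMARD during withdrawal. The same classification feeds the co-primary question, because section 6.2 compares anti-CCP change between clinical responders and non-responders.

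**Working it through.** **Plan's own figure.** Section 3.1 expects 70-80% of 25 patients to reach low disease activity: 25 × 0.70 = 17.5 and 25 × 0.80 = 20. This reproduces the stated 17-20 patients in withdrawal.

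**How the plan as written classifies four patients**

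| Patient | Rule that applies | Counted as |
|---|---|---|
| No steroid, scores low throughout | Score only | Maintained; the label is correct |
| Stable prednisone from entry, scores low throughout | Score only | Maintained; the label omits prednisone |
| Joint injection two weeks before Month 6, score then low | Score only; the 4-week limit does not reach Month 6 | Responder |
| Steroid started or raised during withdrawal, score stays below the flare limits | Score only | Maintained |

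The last two are counting errors against the stated endpoint. The second is a labelling error.

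**How many patients the label could misdescribe.** The documents do not give the share on prednisone. Assume 20-40% of those in withdrawal:

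- lower end: 17 × 0.20 = 3.4
- upper end: 20 × 0.40 = 8.0

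So about 3-8 patients would not be on csDMARD alone. No frequency can be given for injections or dose increases after Day 1. Each patient misclassified for that reason moves the proportion in withdrawal by 1/20 = 5.0 to 1/17 = 5.9 percentage points.

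**Why the effect on the maintenance rate cannot be derived.** With a share s on steroid, the pooled rate minus the steroid-free rate is s × (rate on steroid − rate steroid-free). The documents supply none of these terms. If the two rates are equal, the difference is 0. If they were 60% and 40% (assumed), it would be 0.20 × 20 = 4 points to 0.40 × 20 = 8 points. If patients who need prednisone flare more often, it would be negative.

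**Can the data support a rule?** In all three event tables, as they read in the available text, Medication review is unmarked at Month 6/ET. It is marked at the flare visit and the 4-weekly visits in the table with flare, and at Month 9 in the other two. Table layout can be lost in conversion, so this should be checked against the original schedule.

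**Entry wording.** Sections 4.1 and 4.3 put the oral dose at the equivalent of 10 mg daily; section 5.5 permits less than 10 mg daily. The two do not agree.

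**The case against.** Four arguments on the other side carry weight.

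1. *Prednisone is permitted, not required.* Steroid-free patients can show the endpoint exactly as worded. A reader might infer that the enrolled population cannot demonstrate it at all; the documents do not support that.

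2. *Alone may mean without abatacept.* Section 1.4 contrasts maintenance on MTX with drug-free remission, and the Study Summary contrasts abatacept on with abatacept held. This is a natural reading, but no section states it. If it was intended, the endpoint should say that background steroid is part of the maintained regimen.

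3. *Stable prednisone is a weak explanation for response.* Entry requires active disease (CDAI above 16 or DAS28-CRP of at least 4.0, with at least 3 tender and 3 swollen joints) despite a dose stable for at least 4 weeks. Prednisone that left the disease active is unlikely to be the sole cause of later low disease activity. This stands, and it confines the bias argument to injections and dose increases after Day 1. For stable users the fault is the label.

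4. *This is an exploratory pilot.* Section 6.1 gives no sample size, and section 6.2 specifies no test of maintenance. That excuses missing power. It does not excuse a headline proportion whose name differs from what is counted.

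**Conclusion.** The concern holds as a fault in how successes are counted and labelled. As written, the trial estimates low disease activity maintained on csDMARD with or without corticosteroid, including steroid added after baseline. On the assumption that 20-40% of the 17-20 patients in withdrawal take prednisone, about 3-8 fall outside the stated regimen. The number affected by later injections or dose increases is unknown.

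A reader might go further and put a figure on the overstatement. Suppose 18 enter withdrawal, 9 stay flare-free (50%) and 3-4 of those 9 are on steroid; one might then report 5-6 of 18, or 28-33%. That removes steroid users from the numerator but leaves them in the denominator, so each is treated as a failure. At 20-40% on steroid, 3.6-7.2 of the 18 are users and 10.8-14.4 are not. The steroid-free rate then lies between 5/14.4 = 35% and 6/10.8 = 56%, a range that includes 50%. The documents support neither a size nor a direction for the effect of stable prednisone on the rate.

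**What to change.** In sections 3.1, 3.2 and 6.2:

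- Use one primary success definition. Low disease activity at Month 6, and flare-free status afterwards, count only if the oral steroid dose is no higher than at Day 1 and no IM, IV or IA steroid was given in the 4 weeks before the assessment. This reuses the length of the protocol's own entry window.
- Describe that result as maintenance on csDMARD with or without stable background prednisone.
- Report the same proportion separately in patients on no steroid, with those patients forming both numerator and denominator, and state in advance how and when being on no steroid is judged. Reserve the words csDMARD alone for this line.
- Mark Medication review at Month 6/ET in all three event tables so that the condition can be derived.
- Reconcile the oral steroid wording of sections 4.1 and 4.3 with that of section 5.5.

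The first four changes affect how patients are counted and what is recorded, not how they are treated. The last asks only that the sections agree. The cost is one added medication-review entry, one derived variable and a headline proportion that may be less favourable, because an added condition can only remove successes. The steroid-free line will rest on fewer patients and should be read as descriptive.

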### 3.3 Secondary Study Endpoints

We will correlate the relationships between co-primary endpoints over time and then confirm this relationship by dechallenge of Abatacept after induction of low disease activity at 24 weeks.

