## **2 Study Objectives**

As a step toward a cure, we will directly assess the impact of a treatment on the underlying autoimmune disease process. Because Abatacept has unique mechanisms of action we believe that ABATACEPT treatment ameliorates RA clinical disease activity through beneficial effects on the pathologic breaches in adaptive immunity that are causal for disease. We will therefore conduct a prospective open therapeutic trial with adult seropositive (i.e., ACPA-positive) RA patients and perform intensive quantitative surveys of pathologic autoantigen-specific B cell memory.

We will test whether the clinical benefit induced by ABATACEPT treatment are paralleled by reductions (i.e., normalization) in the in vivo representation of disease-associated anti-citrullinated protein antigen (ACPA) memory B cells after 6 months of treatment. The corollary is to determine whether reductions of disease-associated memory B cells are the most meaningful marker of therapeutic response? ii) Hypothesis 2: The cessation of ABATACEPT treatment (i.e., dechallenge) with continued methotrexate therapy results in clinical flare, is then paralleled by reaccumulation in the bloodstream of disease-associated ACPA memory B cells.

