#### **6.2 *Statistical Methods***

These studies are considered exploratory and will enable power analyses for subsequent larger studies. We anticipate that clinical responders will concurrently have more than 25% decreases in IgG anti-CCP3 levels (ANOVA). The mean change in IgG anti-CCP levels in responders versus non-responders will be analyzed by t-test. A proportional decrease in the estimated level of IgG anti-CCP3 secreting recirculating memory B cells is predicted as well. Clinical non-responders are predicted to not have a significant change. No significant effects on total IgG, IgA or IgM are anticipated. In a recent report with cross-sectional analyses we documented highly significant correlations  $r=0.57$   $p=0.0033$  between ACPA and memory B cell levels in studies of 24 RA patients (11). With longitudinal analyses we anticipate that relationships should require fewer subjects to document correlations between shifts in clinical activity and ACPA IgG and ACPA-memory B cell levels overtime. We will

assess non-parametric paired-sample comparisons by Spearman correlations, and longitudinal measurements using paired t test, with Prism v6.0e (GraphPad, La Jolla, CA). P<0.05 will be considered significant.

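### All patients stop abatacept on the same schedule and flarers are never compared with non-flarers, so a B-cell rise at flare cannot be told apart from a rise due to drug withdrawal.

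*Combined protocol and SAP*

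**What the plan says.** Section 3.1 describes a single-arm study in which each "patient will be their own longitudinal control for the immunomodulatory activity of Abatacept". Blood is collected "at screening and at day 0 after which Abatacept will be initiated in concert with methotrexate or pre-existing csDMARD". The follow-up on treatment is given as "Each patient will then be reevaluated at 3 months and 6 months". Then: "In all patients, Abatacept will be discontinued after 6 months". Enrolment is set by "patient screening will continue until 25 suitable patients are enrolled and started on therapy in the trial", and 17 to 20 of the 25 are expected to enter the dechallenge period.

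Hypothesis 2 in section 2 is that stopping abatacept while methotrexate continues "results in clinical flare, is then paralleled by reaccumulation in the bloodstream of disease-associated ACPA memory B cells". Section 3.3 gives the dechallenge the task of confirming the link: "We will correlate the relationships between co-primary endpoints over time and then confirm this relationship by dechallenge of Abatacept".

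Section 6.2 anticipates "correlations between shifts in clinical activity and ACPA IgG and ACPA-memory B cell levels overtime". It names Spearman correlation, the paired t test, an ANOVA without detail, and a t test of change in IgG anti-CCP in responders versus non-responders, with significance at P<0.05. It does not state the unit of analysis, includes no visit or phase term, and has no comparison of patients who flare with patients who do not.

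**The concern.** The plan expects abatacept to lower both disease activity and the autoimmune B-cell markers. If it does, stopping the drug may let both rise for that reason alone. Patients who remain well off the drug have had the same withdrawal, so they are the natural comparison for asking whether the marker rise goes with flare. A before-and-after test confined to flarers leaves them out. Flare is also defined by a rise in DAS28-CRP or CDAI, so the clinical half of the parallel is built into the selection of those patients.

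The correlation raises a second, conditional issue. If shifts from the on-drug and off-drug periods enter one coefficient, the common course (down on drug, up off drug) produces a positive correlation even when the two measures are unrelated from patient to patient.

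At stake is the inference from the dechallenge. The trial could report that memory B cells track flare when it has shown only that abatacept affects both measures. Section 6.2 intends these results to feed power analyses for larger studies, which would then be sized on the wrong effect.

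**Working it through.** **The plan's own figure.** Section 6.2 cites r = 0.57, p = 0.0033, n = 24. With t = r√[(n−2)/(1−r²)] = 0.57 × √(22/0.6751) = 3.25 on 22 df, two-sided p = 0.0036. At r = 0.575 it is 0.0033, so the figure agrees within rounding. It is a cross-sectional correlation between ACPA and memory B-cell levels. It does not bear on whether changes in either go with flare.

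**Inputs.** From the documents: 25 patients; 17 to 20 entering dechallenge (18 used here); a predicted fall of more than 25% in IgG anti-CCP3 in responders, with a proportional memory B-cell decrease; P<0.05. Assumed, because the documents give no values: SD of log change 0.25 to 0.5, 6 to 12 flarers, the DAS28 shifts below, and two-sided testing.

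**Paired test in flarers.** Suppose all withdrawn patients regain a 25% loss regardless of flare. The mean log change is δ = −ln(0.75) = 0.288. Power comes from the noncentral t with n−1 df and noncentrality δ√n/SD.

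| Flarers | SD of log change | Noncentrality | Significant rise |
|---|---|---|---|
| 6 | 0.50 | 1.41 | 21% |
| 9 | 0.35 | 2.47 | 58% |
| 12 | 0.25 | 3.99 | 95% |

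The marker has no relation to flare in any row. The test is correctly detecting a withdrawal effect.

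**Correlation of shifts.** In the simulation, 25 patients contribute two on-drug intervals and 18 contribute one off-drug interval. DAS28 shifts have means −1.0, −0.8 and +1.0 with SD 0.9. Log-marker shifts are −a/2, −a/2 and +a, with a = 0.288 (25% fall) or −ln(0.85) = 0.163 (15% fall), in every patient. The two measures are independent within patients. Rates of a significantly positive Spearman coefficient, against a nominal 2.5%:

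- On-drug and off-drug shifts pooled: about 49% to 95% for a 25% fall and 18% to 58% for a 15% fall.
- Same data centred by interval: about 2% to 3%.
- On-drug shifts only, off-drug shifts only, or Day 0 to Month 6 change against change: about 2% to 3%.
- No mean drug effect on the marker: about 2% to 3%, even when pooled.

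Two other routes also inflate the rate. Pooling raw levels at months 0, 3 and 6 gave about 10% to 60% for marker falls of 0.25 to 1.0 SD, with disease activity assumed to fall 2 SD. Pooling the two on-drug intervals gave 10% to 22% when 80% of both falls came in the first interval.

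**Power of the missing contrast.** For a 25% difference between flarers and non-flarers among 18 patients, noncentrality is 0.288/[SD√(1/n₁+1/n₂)] on 16 df. With 9 versus 9 and SD 0.35 this is 0.288/0.165 = 1.74, giving 37% power. The range is 19% (6 versus 12, SD 0.5) to 63% (9 versus 9, SD 0.25).

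**The case against.** The strongest reply is that the plan does not commit to the faulty analyses. Section 3.3 describes two steps, correlate and then confirm by dechallenge, and nothing says both phases go into one coefficient. Section 3.2 speaks of clinical response against changes in B-cell parameters, and section 2 sets the time point at 6 months. The word shifts in section 6.2 can therefore be read as change against change, which is valid. This stands. The correlation issue is under-specification, not a demonstrated bias.

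A paired test restricted to flarers is not written out either; it is inferred from Hypothesis 2 and the methods listed. But neither Spearman, an undefined ANOVA nor the responder t test supplies a flarer versus non-flarer contrast. The responder t test is immune to the common schedule, yet covers only IgG anti-CCP, and neither memory B cells nor the dechallenge.

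Section 6.2 also predicts no significant change in clinical non-responders, and section 3.1 provides for patients who never flare. A fall and recovery in all patients is thus a simplification of the simulation, not the plan's claim.

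Finally, sections 6.1 and 6.2 call the study an exploratory pilot. That lowers the stakes. It does not remove the problem, since section 3.3 uses the dechallenge to confirm and section 6.2 sets a significance threshold.

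**Conclusion.** The point holds for Hypothesis 2: as planned, the dechallenge cannot distinguish marker return that goes with flare from marker return that follows withdrawal. If a 25% loss is regained by everyone, a paired test in flarers is significant in 21% to 95% of trials under the assumed SDs and flarer counts.

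For the correlation the point is conditional. Pooling on-drug and off-drug shifts gives a significantly positive result in about 18% to 95% of trials with no patient-level link, provided abatacept moves the mean marker by 15% to 25% in all patients.

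Two stronger conclusions are tempting and unsupported. One is that the planned correlation will come out positive regardless; no section prescribes pooling, and the rate is nominal for a Day 0 to Month 6 change correlation or if the drug has no mean effect on the marker. The other is that 21% to 95% is a false-positive rate; the rise is real in that calculation, and only its attribution to flare would be wrong.

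**What to change.** 1. In sections 3.3 and 6.2, define the relationship as the across-patient correlation of change with change over one interval (Day 0 to Month 6), or fit a model with visit or phase terms. State that on-drug and off-drug shifts are not pooled.
2. Test Hypothesis 2 by comparing marker change since Month 6 in flarers (flare sample) with non-flarers (nearest off-drug sample, Month 9 or exit), accounting for time since last infusion where the data allow. Report an estimate with a confidence interval, and claim that B-cell return parallels flare only from this contrast.
3. First reconcile the schedules in section 3.1. The text has an exit blood draw for patients who do not flare, but the remission or low disease activity table without flare marks neither blood nor disease activity at Week 48-52. The table with flare marks abatacept infusion under the flare and every-4-weeks columns, whereas the text says abatacept is discontinued in all patients after 6 months. Time off drug is not well defined until these agree.

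The cost is mainly analysis wording, plus the schedule correction. The Month 9 sample is already scheduled for non-flarers. Precision is the price: about 19% to 63% power for a 25% difference with 18 patients, and a correlation of about 0.54 needed for 80% power at n = 25. Flare times may also overlap little with Month 9 or exit, which would leave the time adjustment weakly supported.
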